# 1. SCHEMA

#### 2. BACKGROUND & RATIONALE

#### Cohort A

# + Prior RT + Recurrent/Residual Disease

- Any prior combination of surgery/chemo
- Must have received  $\geq 2$  chemo cycles
- ≥ 180 days since completing RT
- $\geq$  7 days since last chemo dose
- To receive **5 Gy x 5**

#### **Cohort B**

# No Prior RT +Recurrent/Residual Disease

- Any prior combination of surgery/chemo
- Must have received  $\geq 2$  chemo cycles
- $\geq$  7 days since last chemo dose
- To receive **6.6 Gy x 5**

# 2.1 Natural History and Management of Pancreatic Cancer

Over 40,000 cases of pancreatic cancer are diagnosed annually in the United States. Despite aggressive combined modality treatment approaches, the five-year survival of patients with pancreatic cancer is still less than 5%. (1) Surgical resection is considered to be the only potentially curative treatment option. (2) However, more than 85% of patients have locally advanced or metastatic disease when initially diagnosed, and treatment paradigms for patients with all stages of disease continue to evolve. Patients with resectable disease have high rates of both local recurrence and distant failure despite aggressive trimodality therapy, and controversy exists regarding whether or not radiation therapy should be included as part of routine postoperative therapy. (3-5) Neoadjuvant external beam radiotherapy is also frequently incorporated into treatment for borderline resectable pancreatic cancer in an attempt to increase the likelihood of margin-negative resection and improve local control. (6) Nonetheless, rates of local recurrence remain high even in patients who have undergone surgery, and more effective strategies to improve local control and to treat locally recurrent disease are needed.

Similarly, the role of radiation therapy in patients with unresectable disease continues to evolve. Unresectable pancreatic cancer is associated with high rates of occult distant metastatic disease; therefore, despite initially promising results associated with immediate chemoradiation in patients with unresectable disease, current treatment standards recommend the use of induction chemotherapy in this setting. (7, 8) For patients with unresectable disease, the use of induction chemotherapy can help to eliminate occult systemic micrometastases and to identify individuals with treatment-refractory distant metastases, who are unlikely to benefit from local therapies such as radiation. A prospective series testing this approach was recently reported by Huguet et al. (7) Patients were initially randomized to gemcitabine or gemcitabine plus erlotinib; those without progression on this regimen were then randomized to capecitabine-based chemoradiation versus chemotherapy alone. Forty percent of initially randomized patients developed progressive disease and did not proceed to the second randomization. Although the study did not demonstrate an overall survival benefit for RT, local failure rates and time to treatment resumption were both significantly improved in the RT arm. Furthermore, in patients with unresectable but localized pancreatic cancer at diagnosis, effective local therapy may play an important role in disease control. Autopsy studies suggest that approximately 30% of pancreatic cancer patients die due to local disease progression, a

statistic that is corroborated by clinical trial reports of local control rates of under 50% in patients with unresectable disease treated with definitive conventional chemoradiation. (9, 10) Pancreatic tumor progression is also associated with significant morbidity, including pain, jaundice, and gastrointestinal tract obstruction. (11)

Periampullary tumors are also frequently treated with radiation therapy. Patients with periampullary tumors have also been included in this trial because of anatomic and pathological similarities to patients with pancreatic cancer and the fact that the treatment paradigm for these cancers is similar to pancreatic cancer. Patients with periampullary tumors also have similar survival and recurrence patterns as patients with pancreatic cancers. (12) Periampullary adenocarcinoma is a rare malignancy, comprising less than 1% of all digestive cancers and occurring at an annual age-adjusted incidence of only 0.3 cases per 100,000 individuals. (13) As a consequence of this low prevalence, few studies have been performed in this population, and patients who fail definitive therapy (surgical resection in association with neoadjuvant or adjuvant CRT/chemotherapy for resectable disease; conventional CRT or chemotherapy for unresectable disease) have limited options for further treatment. (14, 15) Unfortunately, even among patients with resectable periampullary adenocarcinoma, over 50% will recur following definitive treatment (16).

This trial, therefore, seeks to study SBRT as a means of providing patients with borderline resectable, unresectable, or locally recurrent pancreatic/periampullary tumors with an additional treatment option after receiving prior combinations of surgery/chemotherapy.

# 2.2 Rationale for the use of stereotactic body radiation therapy in pancreatic cancer

Recent advances in radiation treatment technology, including improvements in planning systems, patient immobilization equipment, image-guided radiation therapy technologies, and radiation delivery mechanisms, have permitted the development of stereotactic body radiation therapy (SBRT), which permits the intensification of therapy by delivering increased daily doses of radiation to highly focused targets within the body. Several phase II trials of SBRT in patients with pancreatic cancers have been performed, showing that the technique is well tolerated and is associated with improvements in local control rates compared with historical series of conventionally fractionated chemoradiation. Koong et al. used the Cyberknife™ stereotactic radiosurgery system to demonstrate that a single 25-Gy dose stereotactic body radiotherapy (SBRT) was feasible for patients with locally advanced pancreatic cancer. (17) Furthermore, this dose of radiation resulted in near 100% progression free survival and effectively palliated symptoms related to the local growth of pancreatic tumors. Based on this study, the same group also completed a phase II study assessing the efficacy of combining a standard fiveweek course of chemoradiotherapy followed by a stereotactic radiosurgery boost to the primary tumor in patients with locally advanced pancreatic cancer. In this cohort of 19 patients, 100% of tumors were without local progression. However, all patients eventually developed metastases, with a median time to progression of 5.5 weeks. A more recent phase II study treated locally advanced pancreatic cancer patients with induction gemcitabine followed by single-fraction SBRT (25 Gy) and maintenance gemcitabine chemotherapy. In this study, the excellent progression free survival was confirmed from previous studies (81%). The median overall survival was 11.4 months, median time to progression was 9.7 months and the 1 year survival was 50%.(18) There were no significant acute GI toxicities; however, of the 15 patients alive >6 months after Linac

(linear-accelerator)-based SBRT, 7 (47%) experienced Grade 2 or greater GI toxicity, with 2 (13%) of the 15 experiencing Grade 3 or greater GI toxicity.

To decrease the risk of late GI toxicity, subsequent studies have therefore reduced the per-day dose and prolonged the treatment schedule. For example, Hong et al. reported a neoadjuvant regimen delivering 5 Gy x 5 to the pancreatic tumor plus adjacent lymph nodes using proton beam radiation. (19) This regimen was shown to be safe, with no instances of dose limiting toxicity observed and only 4 of 15 patients developing grade 3 toxicity (no patients experienced grade 4 toxicity). Herman et al. recently published the largest phase II study to date of definitive 5-fraction SBRT in pancreas cancer, which reported a median overall survival rate of 13.8 months. (20) The regimen was also well tolerated, with acute and late grade 2 or greater toxicity rates of 2 and 11%, respectively. SBRT was associated with stable quality of life scores and improving pain scores. Similarly, a grade 3 or greater toxicity rate of 7% was reported in an institutional series of 159 patients treated using five-fraction regimens for both borderline resectable and unresectable tumors. (21)

Using the linear-quadratic formulation, the biologically equivalent dose (BED) of the two proposed fractionation schedules are given in comparison to other commonly used schemes (table 1), including conventionally fractionated radiation, which is typically administered in 28 1.8-Gy fractions for a total dose of 50.4 Gy, usually with concurrent capecitabine-, 5-FU-, or gemcitabine-based chemotherapy. While the BED for the 5 Gy x 5 schedule (early/late 37.5/66.7) must necessarily be lower because it will be used in patients who have already been treated with radiation to the pancreatic region, that of the proposed 6.6 Gy x 5 schedule (BED early/late 54.8/105.6) closely approximates that of standard chemoradiation (BED early/late 60/83.3), but without concurrent chemotherapy and treating a smaller tumor margin (0.3 cm vs. ~2 cm). Furthermore, the proposed 6.6 Gy x 5 fractionation schedule has a much lower late BED (105.6 vs. 233.3) with a similar early BED (54.8 vs. 87.5) as the previous 25 Gy x 1 regimen. Finally, the use of five-fraction SBRT regimens may be able to spare circulating lymphocytes from radiation-induced toxicity that is mediated by high radiation doses to circulating blood. As radiation-induced lymphopenia has been linked to inferior overall survival in patients with both unresectable and resectable pancreatic cancers, it is logical to explore potential ways to decrease the risk and severity of this toxicity. (22, 23) Circulating blood dose is directly proportional to radiation field size and fraction number, suggesting that SBRT is a potentially promising strategy to reduce the risk of radiation induced lymphopenia, perhaps leading to improved outcomes, in patients with pancreatic cancer.

Table 1. Comparison of Radiation Fractionation Schemes in Pancreatic Cancer.							
RT Dose	Regional Nodes	Concurrent	Early BED	Late BED			
(Gy)	Treated?	chemo?	(Gy)	(Gy)			
/# Fractions			$(\alpha/\beta = 10)$	$(\alpha/\beta = 3)$			
50.4/28	Yes	Yes	60 Gy	83.3 Gy			
30/10	Yes	Yes	39	60			
25/5	No	No	37.5	66.7			
33/5	No	No	54.8	105.6			
25/1	No	No	87.5	233.3			

# 2.3 Rationale for Selection of Patient Population

As noted previously, local control rates remain unsatisfactory in patients with unresectable pancreatic cancer, up to 30% of whom die with uncontrolled local disease. Local progression of pancreatic cancer can cause distressing symptoms including pain, biliary and gastrointestinal tract obstruction, and pancreatic insufficiency. Furthermore, preliminary data suggest that some patients treated with stereotactic body radiation therapy for unresectable disease achieve sufficient tumor response to proceed to surgical resection; (20) in patients with borderline resectable disease, neoadjuvant SBRT has also been associated with high rates of margin-negative resection. (21)

The development of recurrent pancreatic cancer after definitive treatment with surgery, radiation, chemotherapy, or a combination of these universally portends a dismal prognosis, with the 5-year survival for such patients being 5.6% or less. (24) Unfortunately, this scenario is not uncommon; even among the small number of patients (10-15%) able to undergo potentially curative surgical resection, more than 80% subsequently develop recurrent disease.(25) Following resection, 71-77% develop distant metastases within 2 years, often accompanied by concurrent locoregional recurrence, while up to 30% exhibit isolated locoregional recurrence. (26-29) Patients who develop combined distant/locoregional recurrence have a median survival of 3 months from the time of recurrence, while those with isolated locoregional recurrence have a median survival of 7 months. (28) Locoregional recurrence is, therefore, a common and serious problem both in the setting of metastatic disease and as an isolated entity. Symptomatic manifestations include pain, gastric outlet/small bowel obstruction, portal hypertension, biliary obstruction, and malnutrition. Although survival is determined chiefly by systemic disease control, local control greatly affects quality of life in pancreatic and periampullary cancer patients. (29, 30) Among the majority of patients with pancreatic cancer who present with unresectable disease, chemoradiation is able to transiently stabilize the disease in some patients and to prolong median survival to 8-14 months. (8, 9, 31) Regardless of whether a tumor is resectable or unresectable at diagnosis, the symptoms associated with local recurrence or persistence of disease require swift and effective treatment.

Preliminary data also supports the safety of re-irradiation of the upper abdomen in patients with pancreatic/peri-ampullary tumors who have previously been treated with conventionally fractionated radiation regimens. In 2013, Herman et al. published their institutional experience of re-irradiation in a group of 18 patients. (32) No grade 3 or greater toxicities were reported with a dose of 5 Gy x 5; reported one-year local control rates were 62%, and 57% of patients who had symptoms of pain before treatment

experienced pain relief. This data provides initial support for exploring a 5 Gy x 5 regimen in patients with a history of radiation treatment in the upper abdomen.

Considering the difficulty of surgical re-exploration due to extensive adhesions after previous resection, the risks of surgery and general anesthesia for patients who often have impaired performance status, and the prolonged time course and inferior local control associated with conventional CRT, we propose that SBRT may be a viable alternative treatment option for patients who have failed other modes of therapy through local recurrence or local progression. The paucity of studies focusing on this population and lack of a standardized treatment paradigm for these patients underscore the need for further investigation. The recent studies delineated above suggest that Linac-based respiratory gated SBRT is a safe and promising therapeutic option for pancreatic and periampullary cancers that merits further study in the specific patient population that will be treated using this protocol. However, further investigation of pancreatic SBRT should be performed in patients who have been more heavily pre-treated with intensive chemotherapy regimens such as FOLFIRINOX (5-FU, irinotecan, oxaliplatin), and gemcitabine in combination with nab-paclitaxel, which are currently commonly used in this setting but were not part of the standard approach in the previously cited phase I and II studies of pancreatic SBRT.

# 3. OBJECTIVES

# 3.1 Primary Objective

 To estimate rates of acute (within 3 months of treatment) grade 3 or greater gastrointestinal and hematologic toxicity in patients treated with Linacbased SBRT for pancreatic or periampullary cancers who have previously received other treatment.

# 3.2 Secondary Objectives

- To estimate rates of late (> 3 months after treatment) grade 2 gastritis, enteritis, fistula, and ulcer, or any other grade 3 or greater gastrointestinal toxicity in patients treated with Linac-based SBRT for pancreatic or periampullary cancers
- To estimate rates of local progression, overall survival, metastasis-free survival, and progression-free survival in patients with pancreatic or periampullary cancers treated with fractionated Linac-based SBRT.
- To evaluate the ability of Linac-based SBRT to provide pain control in patients with pain related to a pancreatic or periampullary tumor.
- To evaluate quality of life in patients undergoing treatment with Linac-based SBRT for pancreatic or periampullary cancers.

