#### 3.3.2 Secondary Outcome Measures

• Late (> 3 months after treatment) toxicity rates (as raw percentage), as related to the RTOG Late Radiation Toxicity Grading Scale.

- One-year rates of overall, progression-free, and metastasis-free survival (will
  continue to obtain data on these outcomes at subsequent visits beyond 1
  year, but the 1 year time point will represent the outcome measure of
  interest)
- Pain control at one and three months after treatment (based on reporting of standard pain score (0-10) with an option to record pain score based on FACES assessment scale) –will continue to obtain data on pain control at subsequent visits but these 2 time points will represent the main outcome measures of interest
- Quality of life at each follow-up visit (measured by EORTC QOL-Q scale) will
  continue to obtain data on quality of life at subsequent visits but these 2 time
  points will represent the main outcome measures of interest

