# 8. TOXICITIES TO BE MONITORED/DOSAGE MODIFICATIONS

It is difficult at this time to predict with confidence the percentage risk of complications from the proposed Linac-based SBRT treatment. However, it is reasonable to extrapolate from the current experience with radiotherapy in and around the pancreas. Based upon prior phase I and phase II studies, we anticipate that the toxicities associated with this treatment will be acceptable. We estimate that ≤20% of patients will experience grade 2 or higher late Radiation-related GI toxicity within one year. Late GI toxicities are those events occurring more than 3 months after Linac-based SBRT. Acute GI toxicities are those events occurring within 3 months following Linac-based SBRT. Acute toxicities commonly associated with such treatment include nausea, vomiting, fatigue, anorexia and weight loss. Severe side effects such as gastrointestinal (GI) obstruction, perforation, or hemorrhage are uncommon complications, occurring in <5% of patients undergoing standard radiation therapy for pancreatic cancer. The major serious toxicity in this group of patients is the development of duodenal/gastric ulcers. Most of these are successfully managed medically. However, Stanford has observed 2 cases of duodenal perforation associated with Linacbased SBRT. We anticipate that because of refinements in radiation treatment planning techniques and because the dose will be divided over five treatments (as opposed to one), the biological equivalent and actual dose to the duodenum will be less than prior studies.

Although we expect a comparable rate of complications with fractionated Linac-based SBRT, it is important to note that vomiting, GI obstruction, GI hemorrhage, anorexia and weight loss are also commonly associated with pancreatic cancer progression. Clinical and radiographic assessments will be performed in an effort to identify these effects, ascertain their etiology and provide the most appropriate palliative measures. Hepatic and renal radiation toxicity is not anticipated given the expectation of limited incidental irradiation of these organs and we have not observed any to date in the patients treated with Linac-based SBRT. Complications, if any, will be graded according to the CTCAE, National Cancer Institute, version 4.0 (see Appendix I). We will also utilize the RTOG scale for grading acute and chronic radiotherapy toxicities.

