# 11.10 Analysis of Secondary Objectives

Acute toxicities according to CTCAE 4.0 will be summarized by frequencies and rates calculated as the proportion of patients in the safety population experiencing SAEs, discontinuations due to AEs, and AEs for the two cohorts combined. For the secondary objective of estimating rates of late (> 3 months after treatment) grade 2 gastritis, enteritis, fistula, and ulcer, or any other grade 3 or greater gastrointestinal toxicity, the proportion of patients with each condition and its 90% confidence interval will be calculated.

In Cohort B only, Kaplan-Meier estimates will be used to estimate the median and 90% confidence intervals for time to local progression, overall survival, metastasis-free survival and progression-free survival. The 1-year rates and 90% confidence intervals will be also be estimated from these curves. A listing of clinical outcomes will be generated for Cohort A.

Pain control (based on reporting of standard pain score (0-10) with the option to use the FACES 0-10 scale) will be evaluated before and after Linac-based SBRT and the change in pain scores will be evaluated and summarized through descriptive statistics separately for each cohort. For Cohort B, linear mixed models will be used to model changes in pain over time. A similar approach will be used for the EORTC QOL-Q scale.

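### Sections 3.2 and 11.10 leave late grade 3–5 ulcer, fistula, gastritis and enteritis without a clear place in the late-toxicity endpoint, and no any-event late rate is planned

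*Combined protocol and SAP*

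**What the plan says.** Late toxicity, meaning more than 3 months after treatment, is described in four places.

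- **Section 3.2** sets the secondary objective: to estimate rates of "grade 2 gastritis, enteritis, fistula, and ulcer, or any other grade 3 or greater gastrointestinal toxicity".
- **Section 11.10** repeats that description and gives the analysis: "the proportion of patients with each condition and its 90% confidence interval will be calculated". It names no other late-toxicity summary. Its general summary of AEs and SAEs is introduced as covering acute toxicities.
- **Section 3.3.2** gives the outcome measure as "Late (> 3 months after treatment) toxicity rates (as raw percentage), as related to the RTOG Late Radiation Toxicity Grading Scale". It has no grade cut-off and no list of conditions.
- **Section 8** states an expectation: "We estimate that ≤20% of patients will experience grade 2 or higher late Radiation-related GI toxicity within one year". It also says: "The major serious toxicity in this group of patients is the development of duodenal/gastric ulcers".

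Two further places bear on the point. Section 11.4 assigns safety analyses to everyone who received at least one SBRT session. Section 15 keeps toxicities below CTCAE grade 3 off the AE log and the case report forms, leaving them in the patient chart.

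**The concern.** In a single phrase, grade 3 carries *or greater* and grade 2 does not, and the grade 3 limb is limited to toxicities other than those just listed. An analyst who programs the rule as written has no category for a severe ulcer, fistula, gastritis or enteritis. One who reads for intent counts them. The two would report different late rates from the same data, and the difference would lie in the severe events of the types the protocol singles out.

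Separately, a reader of the results will want to know what share of patients had any qualifying late event. Section 11.10 does not plan that figure, and the planned per-condition figures do not determine it.

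This is a secondary endpoint, but Sections 5 and 11.5 make safety the focus of the trial, so its definition should admit one reading.

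**Working it through.** The plan states no rate or precision for this late endpoint, so there is no planning figure to reproduce. The first two steps are a comparison of text; the last two are illustrative arithmetic.

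**1. Literal rule in 3.2 and 11.10, by event**

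- Late grade 2 ulcer, fistula, gastritis or enteritis: counted in the first limb.
- Late grade 3, 4 or 5 event of those four types: not grade 2, and not another toxicity, so in neither limb.
- Any other late GI event of grade 3 or higher: counted in the second limb.
- Any other late GI event of grade 2: not counted.

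**2. Whether another section settles it**

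- Section 3.3.2 has no grade limit, so a grade 3–5 ulcer falls within it. It gives no numerator and names the RTOG late scale. Sections 3.2 and 11.10 name no scale for late events, and Section 8 invokes both CTCAE 4.0 and RTOG.
- Section 8 speaks of grade 2 or higher, which points to the likely intent. It covers any radiation-related late GI toxicity within one year. Section 3.2 has no attribution limit and no one-year limit, and omits grade 2 events outside the four conditions.
- The stopping rule in Section 11.3 counts treatment-related grade 4–5 AEs within one year. It omits grade 3 and is not the late endpoint.

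The sections therefore give three definitions, and 11.10 implements only that of 3.2.

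**3. What per-condition proportions say about the any-event rate**

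For condition proportions p₁, …, pₖ in the same patients, the any-event rate lies between max(pᵢ) and the smaller of 1 and Σpᵢ. Take N = 38 (Section 11.5) and assume 2 patients in each of five categories: the four named conditions, plus other grade 3 or higher.

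- Each category: 2/38 = 5.3% (90% exact interval 0.9 to 15.7%).
- Complete overlap: any-event rate 2/38 = 5.3%.
- No overlap: any-event rate 10/38 = 26.3% (90% exact interval 15.0 to 40.5%).

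The same table is compatible with anything from 5.3% to 26.3%. The counts are assumed; the example shows only that the composite cannot be recovered.

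**4. Size of the grade-wording effect**

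Each patient moved in or out of the numerator is 1/38 = 2.6 points. The documents do not say how many severe late events to expect in the four conditions.

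- In the single-fraction study in Section 2.2, of 15 patients alive beyond 6 months, "7 (47%) experienced Grade 2 or greater GI toxicity, with 2 (13%) of the 15 experiencing Grade 3 or greater GI toxicity". If both severe events were of the four types (assumption), the literal rule drops them: (7 − 2)/15 = 33.3% instead of 7/15 = 46.7%. If neither was, nothing is lost.
- The five-fraction phase II study in Section 2.2 is closer in schedule, "with acute and late grade 2 or greater toxicity rates of 2 and 11%, respectively". In 38 patients, 0.11 × 38 = 4.2 with a late event of grade 2 or greater. The document gives no split by grade or condition, so anywhere from none to all of them could be affected.

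**The case against.** The strongest reply is that this is drafting shorthand. A grade 3 ulcer can be read as *other* than the listed grade 2 items. The protocol drops *or greater* elsewhere without meaning to: Section 3.3.1 says grade 3 for the primary outcome, where Sections 3.1 and 11.9 say grade 3 or greater. Sections 3.3.2 and 8 point the same way. This stands as evidence of intent. It does not remove the ambiguity from the analysis rule, and it supports writing the intent down.

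A reader might infer that severe late ulcers escape the trial's safety monitoring. The documents do not support that. Grade 3 and higher events are outside Section 15's recording exemption, SAEs are collected until death or hospice (Section 15.3), and treatment-related grade 4–5 events within one year feed the stopping rule. The gap is in one secondary tabulation.

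A reader might also infer that no patient-level late rate is produced. The per-condition figures are already proportions of patients; what is missing is the any-event figure. The plural *rates* in Section 3.2 is consistent with per-condition reporting, so the composite is an addition and not a broken promise.

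Finally, a reader might treat the any-event rate as the quantity behind Section 8's 20%. It is not, even after rewording, for the reasons in step 2 of the working. Nor does any test or decision in the plan use the 20%.

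**Conclusion.** The point holds as an ambiguity in a secondary safety endpoint, together with a missing summary. Taken literally, 3.2 and 11.10 leave late grade 3–5 events of the four named types uncounted; the likely intent is grade 2 or greater. No any-event late rate is planned, and none can be derived from the planned figures.

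The effect cannot be estimated from the documents. It is tempting to apply the 7% and 13% grade 3 or higher rates in Section 2.2 to 38 patients (0.07 × 38 = 2.7 and 0.13 × 38 = 4.9) and infer a loss of 7 to 13 points. That is not supported. The 7% is not stated to be late or GI-specific. The 13% is 2 of 15 patients alive beyond 6 months after 25 Gy in one fraction, a schedule with a late BED of 233.3 Gy against 105.6 Gy for 33 Gy in five fractions (Table 1). The upper figure of 4.9 severe cases exceeds the 4.2 expected at grade 2 or greater from the closer five-fraction study. The calculation would also need most severe events to be of the four types, which no section states.

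That a worse safety profile could yield a lower reported rate is true only if the literal reading is adopted.

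**What to change.** 1. In Sections 3.2 and 11.10, define the endpoint as *late gastritis, enteritis, fistula or ulcer of grade 2 or greater, or any other gastrointestinal toxicity of grade 3 or greater*.
2. In Section 11.10, add the proportion of safety-population patients with at least one qualifying late event, with its 90% exact confidence interval, ahead of the per-condition table.
3. Align Section 3.3.2 with this definition, and name one grading scale for late events throughout.
4. If the result is to be compared with Section 8's expectation, add a separate tabulation of any radiation-related late GI toxicity of grade 2 or higher within one year.
5. Amend Section 15 so that late grade 2 GI events are entered on the case report forms. Section 12 lists follow-up toxicity data without a grade limit, but Section 15 expressly excludes events below grade 3. Without this change, item 4 and the grade 2 part of the endpoint would depend on chart abstraction.

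Items 1 to 3 cost a few lines of text and one table row. Items 4 and 5 add a table and a small amount of data entry, with chart review for patients already followed. The reported late rate may come out slightly higher.
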